Title: Stand if You Can: A Standing Intervention in Long Term Care

NCT Number: NCT03796039.

Version Date: May 1 2020

METHODS

Study Setting

The *Stand if You Can* trial is a multi-center, parallel group, RCT using intention-to-treat analysis. For pragmatic reasons, this trial is a single blinded study. It will take place in four different LTC facilities within two cities in the Province of New Brunswick, Canada. Two of the selected facilities will be in each city. Each facility is designated by the Province of New Brunswick as a level three LTC facility (1). This means that the clients have health limitations which require assistance and supervision on a 24-hour basis (1,2). Three of the four facilities are sister nursing homes, meaning they follow the same policies, similar procedures, and have identical floor plans. Registered nurses, licenced practical nurses and rehabilitation assistants are regular staff at all the participating homes. Each of the chosen LTC facilities have the space and resources necessary to assist in the operation and delivery of the trial.

Participant timeline

All of the outcome variables, and participant characteristics will be collected at pre (T1) and post (T2) testing. Data regarding fall information will have two additional data collection time points, including 6 months prior to the intervention (-T) and 6 months follow-up (T3). Attendance will be collected during the intervention, between T1 and T2. See Figure 1 for timeline.

Eligibility Criteria

Inclusion criteria:

- 1) Participants must be a resident of one of the four participating LTC facilities at the time of recruitment.

- 2) Participants must be able to provide consent or have Substitute Decision Maker agree on their behalf to participate in the study if required.
- 3) Participants must be able to walk for 10 meters, with or without a walking aid.

Exclusion Criteria:

- 1) Residents identified by the LTC facility's rehabilitation staff as being too high risk for falling, or unable to participate for safety reasons.

Interventions

Social Standing Intervention

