Metabolic profile will be assessed as participant high-density lipoprotein, low-density lipoprotein, total cholesterol, triglyceride, and blood glucose using a CardioChek Professional Analyzer system (PTS Diagnostics, Whitestown, Indiana, USA). Following a finger prick conducted using a single use lancet, approximately 60 μ L of whole blood will be collected. Forty μ L will be used to assess blood lipids via a Lipid Panel (PTS Diagnostics, Whitestown, Indiana, USA), with the remaining 20 μ L used to assess blood glucose via a Glucose Panel (PTS Diagnostics, Whitestown, Indiana, USA).

Cognition will be assessed using the Mini-Mental State Examination (MMSE) questionnaire(6). Participants who score 18 or above will be asked to complete subsequent questionnaires pertaining to their psychosocial health. These questionnaires include the Geriatric Anxiety Inventory(7), Falls Efficacy Scale – International (FES-I) (8), Geriatric Depression Scale Short Form (9), the DeJong Loneliness Scale (10) and the UCLA Loneliness Scale (11).

Falls, injuries due to falls, and hospitalization will be collected from the participants accident report provided by the LTC facility. At 6 months follow-up, data will be collected retrospectively from 6 months prior to the intervention and up until the 6-month follow up. This data includes the number of falls, type and number of injuries as well as the number of hospital visits.

Attendance will be collected throughout the intervention. The daily total standing time, number of breaks, the use of an assistive device as well as the group size will be recorded.

Sample Size

Sample size was estimated based on anticipated changes in gait speed, the primary outcome of this trial. The minimum clinically important difference in gait speed is 0.1 m/sec

(18). With a cluster size of two, and assuming a small-to-moderate clustering effect (intraclass correlation coefficient = 0.075), within-group standard deviation of 0.10 m/s, and alpha = 0.05, recruiting 36 participants per group will provide 80% power to detect a clinically important change in gait speed. To account for an expected loss to follow-up of 20%, we plan to recruit 44 participants per group (total n=88).

Recruitment

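### A 20% loss from 44 per group leaves 35.2, just under the stated 36: a minor inconsistency in the attrition allowance, with almost no effect on the stated power

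*Combined protocol and SAP*

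**What the plan says.** In the Combined protocol and SAP, the Sample Size section bases the calculation on gait speed and concludes that "recruiting 36 participants per group will provide 80% power to detect a clinically important change in gait speed". It then adds an allowance for attrition: "To account for an expected loss to follow-up of 20%, we plan to recruit 44 participants per group (total n=88". It does not show how 36 becomes 44.

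On clustering, the same section writes "With a cluster size of two, and assuming a small-to-moderate clustering effect" and gives "intraclass correlation coefficient = 0.075". Study Setting describes the sites: "It will take place in four different LTC facilities within two cities in the Province of New Brunswick, Canada". Allocation describes 1:1 randomisation by cluster. The Statistical Analysis section says that missing values will be estimated by the models.

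**The concern.** An attrition allowance should leave the required number after the expected loss has occurred. Here the required number, the loss rate and the recruitment target stand next to each other, and the third does not follow from the first two if the loss is taken off the recruited number. Multiplying by 1 plus the loss rate, where one should divide by 1 minus the loss rate, is a common slip, and 44 is the value that it would give.

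At stake is the accuracy of two headline figures, the recruitment target and the power. Readers will check them and a report is likely to repeat them.

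**Working it through.** **Inputs** (Sample Size section unless noted)

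- Difference: "The minimum clinically important difference in gait speed is 0.1 m/sec".
- SD and alpha: "within-group standard deviation of 0.10 m/s, and alpha = 0.05". Sidedness is not stated; two-sided is assumed.
- Power 80%, ICC 0.075, loss 20%, 36 needed and 44 recruited per group.
- Facilities: four in total (Study Setting), randomised 1:1 by cluster (Allocation), so two per arm. Equal numbers per facility are assumed.

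**Step 1: reproduce 36.** Without clustering, the normal approximation gives

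n_ind = 2 × (1.96 + 0.8416)² × (0.10/0.10)² = 15.70 per group.

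With two facilities per arm, each facility holds n/2 participants and the design effect is DE = 1 + (n/2 − 1) × 0.075. Solving n = n_ind × DE for n gives

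n = 15.70 × 0.925 / (1 − 15.70 × 0.075/2) = 35.30, rounded up to 36.

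This is the plan's figure. Two other readings fail. Two residents per cluster, taken literally, gives 15.70 × 1.075 = 16.9, so 17. One-sided alpha with two facilities per arm gives 21.3, so 22. Of the readings checked, only two facilities per arm with two-sided alpha reproduces 36.

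**Step 2: apply the 20% loss.**

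- 44 × 0.8 = 35.2 per group (88 × 0.8 = 70.4 in total, against 2 × 36 = 72).
- Largest loss that leaves 36: 1 − 36/44 = 8/44 = 18.2%. A ninth loss leaves 35 (9/44 = 20.5%).
- Target that keeps 36 after 20% loss: 36/0.8 = 45 per group, 90 in total.
- For comparison, 36 × 1.2 = 43.2, rounded up to 44.

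**Step 3: power at the retained numbers.** The z power is Φ(√(n_eff/2) − 1.96), with n_eff = n/DE and the difference equal to one SD. The last column uses the same inputs in a t test on 2 df, with the facility as the unit.

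| Retained per group | DE | n_eff | Power, z | Power, t on 2 df |
|---|---|---|---|---|
| 36 | 2.275 | 15.82 | 80.3% | 35.4% |
| 35.2 | 2.245 | 15.68 | 79.95% | 35.2% |
| 35 | 2.2375 | 15.64 | 79.9% | 35.1% |

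The attrition arithmetic therefore costs about 0.4 percentage points by the plan's own formula (80.3 − 79.9). The cost is small because clustering makes each further participant in the same two facilities worth little: going from 35 to 36 raises n_eff by only 15.82 − 15.64 = 0.18.

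**The case against.** The strongest reply is that 44 may come from correct division. The unrounded requirement is 35.30, and 35.30/0.8 = 44.13, which is 44 to the nearest integer. Measured against 35.30, the 35.2 left after loss is short by only 0.1 participant per group. This stands as far as the mechanism goes: a reader might infer that the plan multiplied by 1.2, but the documents show no formula and both routes fit. It does not remove the inconsistency. Getting from 35.30 to 36 requires rounding up, and rounding 44.13 up gives 45. The text also applies the allowance after stating 36.

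A second reply is that the models will estimate missing values, so lost participants still contribute. The Sample Size section nevertheless inflates for loss, so it treats the retained number as the one that carries the power. Gait speed is measured only at pre and post testing, so a participant lost before post testing has no later gait speed measurement.

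A third reply is that the reading of the cluster wording is ours. That is so. Taken literally the requirement would be about 17 per group and 44 would be ample, but the plan's own 36 would then be unexplained.

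Two stronger readings are tempting and should be resisted. One is that the trial loses its 80% power through this arithmetic; at 35 per group the power still rounds to 80%. The other is to count the lower figures from t critical values as a result of attrition. With a t test on 2n − 2 df, power is already 79.2% at the full 36 (78.7% at 35), and the facility-level figure is about 35% at either number. Those gaps come from the choice of reference distribution and from the small number of facilities.

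**Conclusion.** The point holds as a minor inconsistency in a stated figure. Taken at face value, 44 per group keeps 36 only if loss is at most 18.2%; keeping 36 after 20% loss takes 45 per group. The shortfall in the recruitment target is one participant per group, two in total.

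That part is simple arithmetic on the plan's figures and does not depend on how 44 was derived. The power figures rest on two-sided alpha, two equal-sized facilities per arm and the normal approximation. On that basis the effect is about 0.4 points, and the documents do not support calling it underpowering.

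A separate matter, not caused by attrition, is much larger. The 80% rests on a normal approximation that takes no account of there being only two facilities per arm. Recruiting 45 would correct the arithmetic but would leave facility-level power at about 35%, so the correction should not be read as securing 80%.

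**What to change.** Reword the attrition sentence in one of two ways:

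- Keep 44 per group (88 in total) and state that it tolerates about 18% loss, or that a 20% loss leaves about 35 per group with about 79.9% power by the plan's own formula.
- Give 45 per group (90 in total) as the target that keeps 36 after 20% loss.

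In either case, show the inflation formula and say that the calculation uses two facilities per arm. As a separate sentence, state that the 80% comes from a normal approximation that ignores the small number of facilities, and that a facility-level t test on 2 df gives about 35% power on the same inputs.

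The first option costs a few words and leaves recruitment unchanged. The second adds two participants. The sentence on facility-level power costs no more to write, but it makes the stated power visibly less favourable.

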Participants residing in one of the facilities randomized to the intervention will be offered up to 100 minutes of supervised standing per week, for 22 weeks. To achieve 100 minutes of standing each week, participants will stand (either on their own or with a group of their peers) for ten minutes at a time, twice per day, five days per week (Monday-Friday). Participants will be allowed up to five breaks per session of undefined length to assist in attaining the objective of 100 minutes of standing per week. During the standing time research assistants (RA) will engage socially with the participants, with a 1:4 ratio of RA and participants. If the LTC facility is hosting a stationary group activity during the standing time participants will be allowed to partake, provided they can do so while standing. If a participant is able, they will be allowed to stand for 20 consecutive minutes by week 11 and onward, as opposed to two separates 10-minute sessions. The opportunity to have two separate sessions will still be an option for those who do not wish to stand for 20 minutes in one session. A session will be terminated if the maximum time is reached, if the participant takes all five permitted breaks, or if the participant requests to stop or shows signs of physiological distress. Participants will be encouraged to stand five days each week. However, if the participant displays strong verbal disinterest, refuses participation, is

non-compliant, or is physically unable to attend, they will be allowed to miss the planned session. Participants will not be excluded from the study or subsequent analyses due to non-compliance to the intervention. Following a request from a consenting participant, LTC facility staff, or the Substitute Decision Maker will a participant no longer be asked to participate in the standing sessions. Adherence to the intervention will be monitored and tracked using a daily log. Participant attendance, total standing time, number of breaks taken, and total group size (if applicable) will be recorded at each session. These logs will be kept at the local research institution and brought to the LTC facility by RAs each day.

Social Exposure (control)

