Participants residing in the control facilities will spend 20 consecutive minutes engaging in social activities with the RA. Social activities will be structured similarly to the intervention group. Some examples include sharing jokes and stories, playing charades, and signing along to music. Social activities will be completed in groups or individually, with participants allowed to join the activity by whatever means of transportation they chose. There will be no limit to the number of participants allowed to attend each group social activity session, with the number of staff ranging from one to two. Adherence to the social activity will be monitored and tracked using a daily log noting attendance, total group size (if applicable), the length of the activity. These logs will be kept at the local research institution and brought to the LTC facility by RAs each day.

Variables and Measures

Participant Characteristics

Participant age, sex, height, weight, medical condition, length of stay in the LTC facility, transfer status, and frailty status will be collected from LTC staff at pre-testing (T1) and post-testing (T2) using the most recent data from participants' LTC health records.

Primary outcome

The primary outcome of this study is gait speed. To measure gait speed, participants will perform a 10-meter walk at pre and post testing, with the first and last two meters used as acceleration and deceleration zones. Gait speed will be measured over the intermediate 6 meters. If required, participants will be permitted to use an assistive device while closely monitored by RA with an available wheelchair made available for safety. Participants will be instructed to walk at a comfortable speed and to start walking when signalled. Using a stopwatch, a RA will manually start timing the participant once the participant's foot or walking aids crosses the 2-meter mark, whichever occurs first. The timer will be stopped once the participant or the walking aid reaches the 8-meter mark and the total time will be recorded in seconds. Once a participant completes the first trial, the participants will take a brief pause and a second trial will be completed. The average of the two values will be used for analysis.

Secondary Outcomes

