The Director of Care for each of the LTC facilities will be contacted to aid in the identification of residents who may benefit most from a low-intensity physical activity intervention. A letter will be sent from the LTC facility on behalf of the research team to each potential resident, or their Substitute Decision Maker to inform them of the study. Once the letters are distributed members of the research team will contact residents or their power of attorney to formally inquire about participation and obtain informed consent for participation.

Allocation

RAs not participating in the trial procedures will use a random number generator to construct a permuted-block randomisation list (block size = 2). All participants will be cluster-randomized to the intervention or control group on a 1:1 basis. Group assignments will be concealed from participants, outcome assessors, and research staff completing the data analyses. RA's conducting pre-testing evaluations will be blinded at pre-testing, but will conduct post testing evaluations unblinded, due the diversity of evaluations requiring training and experience.

Data Management

Each participant will be assigned an ID number. All the data collected will be recorded under this number in their participant file. Each file will have the data manually written, and then transferred from the files into an excel on password protected computers. The data will be entered and revised by two different RAs to reduce potential data entry errors. Only researchers engaged in collection, analysis and dissemination will have access to data, with approval of the primary investigators. Hard copies of the collected data will be stored in filing cabinets, in a locked working space at each university. Data will be kept for a period of seven years, at which point it will be destroyed.

Statistical Analysis

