As this is an intention to treat trial, all data will be evaluated based on the randomized group allocation. Generalized linear models – specifically an ANOVA analysis, will be used to compare the dependant variable (gait speed) between intervention groups while accounting for potential confounders (e.g., age, sedentary level). Secondary outcomes such as sedentary behaviour, leg strength, sit to stand ability, balance performance, psychosocial outcomes, and blood lipids and blood glucose will each be analyzed with separate linear models as well, in relation to intervention group. Consistent with an intention-to-treat approach, the models will estimate missing values. When possible, general linear models will also be used to evaluate subgroup analyses, where health conditions will be considered a fixed variable in relation to gait speed performance.

1. Standards Manual: Nursing Home Services. Department of Social Development, Government of New Brunswick; 2019.
2. Banjeer A. An Overview of Long-Term Care in Canada and Selected Provinces and Territories. Place Call Home Long Term Care Can. 2009;29–57.
5. C. X. Yang. Low-Cost Experimental System for Center of Mass and Center of Pressure Measurement (June 2018). IEEE Access. 2018;6:45021–33.
10. De Jong Gierveld J, Van Tilburg T. The De Jong Gierveld short scales for emotional and social loneliness: tested on data from 7 countries in the UN generations and gender surveys. Eur J Ageing. 2010/04/09 ed. 2010 Jun;7(2):121–30.

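### Facilities are randomised, but the planned gait-speed ANOVA makes no allowance for clustering: type I error is about 20-23% at the plan's own ICC of 0.075

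*Combined protocol and SAP*

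**What the plan says.** **Unit of randomisation.** The intervention section describes "Participants residing in one of the facilities randomized to the intervention". The control section likewise says "Participants residing in the control facilities will spend 20 consecutive minutes" in social activity. The Allocation section specifies a "permuted-block randomisation list (block size = 2" and states "All participants will be cluster-randomized to the intervention or control group on a 1:1 basis". Study Setting gives four facilities, two in each of two cities.

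**Sample size.** The target difference is 0.1 m/s, the within-group SD 0.10 m/s and alpha 0.05, "assuming a small-to-moderate clustering effect (intraclass correlation coefficient = 0.075". The result is that "recruiting 36 participants per group will provide 80% power to detect a clinically important change in gait speed", raised to 44 per group for 20% loss.

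**Analysis.** The Statistical Analysis section says "specifically an ANOVA analysis, will be used to compare the dependant variable (gait speed) between intervention groups", adjusting for confounders of which age and sedentary level are given as examples. The secondary outcomes get separate linear models by intervention group. Neither that section nor any other says how clustering will enter the analysis.

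**The concern.** Residents of one home share staff, routines and admission patterns, so their outcomes tend to be correlated. The plan accepts this when it sizes the trial. An ANOVA that treats residents as independent takes its error term mainly from variation within homes, whereas the arm contrast varies with differences between homes. The standard error, confidence interval and p-value of the primary comparison are then too small, and a chance difference between two pairs of homes can be reported as an effect of standing.

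Adding facility as an ordinary fixed covariate would not help, because facility is nested in arm. Adjusting for age or sedentary level may shrink the residual ICC but cannot be relied on to remove it.

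**Working it through.** **1. Inputs.** From Sample Size: difference 0.1 m/s, SD 0.10 m/s, ICC 0.075, alpha 0.05 (two-sided assumed), 80% power, 36 evaluable and 44 recruited per group. Two facilities per arm is an inference from four facilities, 1:1 allocation and block size 2. That gives m = 36/2 = 18 or 44/2 = 22 residents per facility.

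**2. Reproducing the plan's figure.** Without clustering, n = 2 × (1.960 + 0.8416)² × (0.10/0.1)² = 15.70 per arm. With two clusters per arm, m = 15.70 × (1 − 0.075) / (2 − 15.70 × 0.075) = 17.65 using the unrounded n, so 18 per facility and 36 per arm, as stated. The section gives the cluster size as 2. If that meant two residents per cluster, the result would be 15.70 × 1.075 = 16.9, or 17 per arm, which does not match. The sample size therefore supports the reading of two facilities per arm.

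**3. Type I error of the participant-level test.** The variance of the arm difference is inflated by the design effect DE = 1 + (m − 1) × ICC, which the ANOVA ignores. Approximately, the true error is 2 × [1 − Φ(1.96/√DE)].
- m = 18, ICC 0.075: DE = 1 + 17 × 0.075 = 2.275; 1.96/1.508 = 1.30; error 19.4%.
- m = 22, ICC 0.075: DE = 1 + 21 × 0.075 = 2.575; 1.96/1.605 = 1.22; error 22.2%.

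Simulation of the ordinary two-group test (400,000 trials per setting, normal data, equal facility sizes):

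| Residual ICC | 18 per facility | 22 per facility |
|---|---|---|
| 0 | 5.0% | 5.0% |
| 0.01 (assumed) | 7.0% | 7.5% |
| 0.02 (assumed) | 9.1% | 10.0% |
| 0.05 (assumed) | 15.3% | 17.4% |
| 0.075 (the plan's) | 19.8% | 22.8% |

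With two individual-level covariates in the model, the error at ICC 0.075 is 18.9% and 22.8%.

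**4. What valid or partly valid tests deliver at ICC 0.075.** The standard error of the difference in facility means is √[0.01 × (0.075 + 0.925/18)] = 0.0356 m/s, so the noncentrality is 0.1/0.0356 = 2.81.
- Facility means, 2 df: type I error 5%; power 35% (m = 18) or 37% (m = 22), with a ceiling near 50% however many residents are enrolled.
- City-paired, 1 df: type I error 5%; power 17% or 18%.
- Participant-level test with variance inflated by 1 + (m − 1) × 0.075: power 80% (m = 18). Its type I error is about 1% at a true ICC of 0.01-0.02, about 5.5% at 0.075 and 8% at 0.10.
- Random-intercept model, m = 18: type I error about 0.3% if 2 df are forced, 7% if the df follow the fit (the facility variance is estimated as zero in 33% of trials), and 11% with a Wald z test.
- Permutation test: six possible 2 v 2 splits give a smallest two-sided p of 2/6 = 0.33. Two blocks of two give four allocations and 2/4 = 0.50.

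**The case against.** **The covariate list is open.** This is true: the confounders are only examples, so the plan does not rule out a facility term. A reader might infer that the plan rejects any clustering adjustment; the text is silent and does not say that. The silence still matters. The only named test is a participant-level ANOVA, and a fixed facility term would not supply a valid error term for arm.

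**The residual ICC may be far below 0.075.** That is possible. The 0.01-0.02 range is an assumption, and even there the error exceeds 5%.

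**The remedy costs most of the power.** This stands and should be stated openly. The limit comes from having four facilities; changing the wording cannot remove it. The extra precision of the unadjusted ANOVA is not real. Inflating the variance at ICC 0.075 is the smallest reconciliation with the sample size, and choosing between it and a facility-level test is a judgement for the trial team.

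**Only three of the four homes are sister homes.** A reader might infer that the fourth home pushes the error well above 23%. The documents give no gait-speed difference between homes. Differences between homes are already part of what an ICC of 0.075 represents, so an added offset would be variance beyond the plan's own value.

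**Conclusion.** The concern holds. Followed as written, the primary test has a type I error of about 20-23% at the plan's own ICC, and about 7-10% at assumed residual ICCs of 0.01-0.02. The sample size pays a design effect of about 2.3 for clustering, and the analysis ignores it. The secondary linear models share the omission, but its size there is unknown because no ICC is given for them.

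The figures rest on two facilities per arm (inferred), equal facility sizes and roughly normal data.

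A reader might also infer that the 80% power figure is an arithmetic error. It is not: 36 per group reproduces. The 80% does, however, treat the ICC as known at 0.075 and takes no account of having only 2 between-facility degrees of freedom.

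**What to change.** **Statistical Analysis.** Pre-specify, for gait speed and the continuous secondary outcomes, an analysis that respects facility randomisation, and state its degrees of freedom. One example is a comparison of covariate-adjusted facility means on 2 df, or on 1 df if the blocks of two are the two cities. Say which applies. Report the facility means and the estimated ICC.

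A participant-level test with variance inflated by 1 + (m − 1) × 0.075 can be reported if labelled as valid only when the ICC is no larger than 0.075. If a random-intercept model is chosen, state its df rule. A permutation test cannot reach significance.

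**Sample Size.** State that the 80% holds only if the ICC is treated as known at 0.075, and give the power of the test actually chosen.

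**Cost.** The text change is short; the statistical cost is large. At ICC 0.075 and 36 per arm, the mean 95% confidence interval half-width is about 0.136 m/s for the 2-df test and 0.36 m/s for the 1-df test. It is about 0.046 m/s for the unadjusted ANOVA and 0.069 m/s for the variance-inflated test. A non-significant result could not be read as no effect.

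The 5% rate of the 2-df test assumes roughly normal facility means with equal variance, which cannot be checked with two per arm. It also assumes no large city difference if allocation is not blocked by city: at an assumed city SD of 0.05 m/s, the rate rises to about 8%.

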Physical activity and sedentary behavior will be tracked for seven consecutive days at pre and post testing using an activPAL (PAL Technologies LTD., Scotland, UK). The activPAL will be placed mid-thigh and held in place using TegadermTM tape. Participant sedentary time, upright time, stepping time, total number of steps and total transitions from sitting to standing will be recorded. ActivPAL data will be considered valid if the participant wears the device over at least four consecutive days(3).

Leg power will be assessed using the 30-Second Chair Stand at pre and post testing, following the Senior Fitness Test protocol (4). Participants will be seated in a standardized, armless chair with their arms crossed across their chest. The participant will stand completely and return to a seated position as many times as possible in 30 seconds. RAs will provide guidance as needed during the test for those with cognitive impairments. If participants are unable to complete the test following protocol, their score will be recorded as 0.

Isometric lower leg strength will be assessed using a handheld dynamometer (Lafayette Hand-Held Dynamometer, Lafayette Instrument, Sagamore, USA) at pre and post. The dynamometer will be positioned mid-tibia, with the padding snug against the participant's leg. To ensure each participant experiences the same resistance throughout the test, RA will use a non-elastic woven strap that will interlace around the handle of the dynamometry and chair leg. With arms crossed across their chest, participants will then be instructed to extend their leg as forcefully as possible into the dynamometer for 10 seconds, with peak strength recorded as maximal kilograms (kg) achieved. Leg strength will be assessed twice on each leg, with an additional trial if the first two differ by more than one kg. RA will provide motivational cues and encouragement during each test.

Balance will be assessed using the BrainBlox software (5)on a Wii Balance Board (Nintendo, Kyoto, Japan) at pre and post testing. The balance board measures ground reaction forces that are then computed into centre of pressure measures. Participants will conduct three trials of 30 seconds with eyes open. Participants will stand in a neutral position, feet hip-width distance apart with their arms at their sides. The balance assessment will be conducted three times, with intermittent breaks as needed. If required, participants will be permitted to use an assistive standing device.

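### The primary analysis should name the gait-speed variable analysed, commit to T1 gait speed as a covariate, and take every covariate at T1

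*Combined protocol and SAP*

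**What the plan says.** Under Participant timeline, "All of the outcome variables, and participant characteristics will be collected at pre (T1) and post (T2) testing". Under Primary outcome, "participants will perform a 10-meter walk at pre and post testing"; the averaging described there is over two walks within one visit, so it does not settle which visit is analysed. Allocation is by home: "Participants residing in one of the facilities randomized to the intervention will be offered up to 100 minutes of supervised standing per week".

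The Statistical Analysis section is the only analysis text. It plans an ANOVA that "will be used to compare the dependant variable (gait speed) between intervention groups while accounting for potential confounders (e.g., age, sedentary level"). It adds separate linear models for the secondary outcomes, sedentary behaviour among them, and says that the models will estimate missing values.

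The Sample Size section comes nearest to naming the analysed variable: "Sample size was estimated based on anticipated changes in gait speed, the primary outcome of this trial". That points towards change. It is a basis for the sample size, however, not a definition of the analysis, and the section does not say whether its SD of 0.10 m/s describes T2 values, change or a residual.

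**The concern.** Three analyses fit the text: T2 gait speed alone, change from T1, and T2 adjusted for T1. They give different estimates from the same data, so the choice could be made after the data are seen. The Allocation section has post-testing done unblinded, which adds to the case for fixing the analysis beforehand.

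The covariates are open in the same way. The list is given only by example. Sedentary level is measured at both visits and is an outcome that a standing programme may alter. Adjusting for its T2 value could remove part of the effect that the trial is meant to estimate.

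With four randomised homes, the arms can differ noticeably at T1 by chance. They could also differ systematically if residents are recruited after homes are allocated. The Recruitment section has Directors of Care help identify the residents expected to gain most, and does not say whether consent comes before allocation.

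**Working it through.** **1. Inputs.** From Sample Size: difference 0.10 m/s (the MCID), SD 0.10 m/s, ICC 0.075, alpha 0.05 (two-sided assumed), 36 per arm. From Study Setting: four homes, read as two homes of 18 per arm. The T1–T2 correlation r is not in the documents, so ranges are assumed.

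**2. The plan's own figure.** Without clustering, n = 2 × (1.960 + 0.842)² × (0.10/0.10)² = 15.70 per arm. With two homes per arm, n = 15.70 × 0.925 / (1 − 15.70 × 0.075/2) = 35.3, rounded up to 36. The design effect is 1 + 17 × 0.075 = 2.275, and the standard error is 0.10 × √(2 × 2.275/36) = 0.0356. The normal formula then gives power 80.3%, matching the planned 80%. Reading the stated cluster size as two residents per cluster gives only 17 per arm.

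**3. Unadjusted power with four homes.** A comparison of home means has 2 degrees of freedom. With noncentrality 0.10/0.0356 = 2.81, power is 35%. This is the reference for what follows.

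**4. T1 adjustment, same r within and between homes.**
- If 0.10 is the SD of change and the comparator is change, the variance factor is (1 − r²)/(2(1 − r)) = (1 + r)/2. At r = 0.7, 0.8, 0.9 this is 0.85, 0.90, 0.95, and power is 40%, 38%, 37%.
- If 0.10 is the T2 SD and the comparator is T2-only, the factor is 1 − r². At r = 0.5, 0.7, 0.8 this is 0.75, 0.51, 0.36, and power is 43%, 55%, 68%.

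**5. Different r between homes (second reading).** The between-home share of home-mean variance is B = 0.075/(0.075 + 0.925/18) = 0.593, so W = 0.407. With the slope equal to the within-home correlation rw, and between-home correlation rb, the ANCOVA factor is B(1 + rw² − 2·rw·rb) + W(1 − rw²).
- rw 0.7, rb 0.25: factor 0.884, power 39%.
- rw 0.7, rb 0: factor 1.092, power 33%.
- rb 0, rw from 0.3 to 0.9: factor 1.017 to 1.151, a variance rise of 2–15%.
- Break-even against T2-only: rb = rw(B − W)/(2B), which is 0.05 to 0.14 over the same range.

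Against change, the comparator's factor is 2B(1 − rb) + 2W(1 − rw). At rw 0.7 and rb 1 it is 0.244, against 0.261 for ANCOVA, so change is then slightly better.

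**6. T2-only against change.** With complete pairs, (T2 difference) − (T2 difference − T1 difference) = T1 difference. Take a normal model with unrestricted allocation of unrelated homes.
- Cross-sectional SD 0.10: the T1 difference has SD 0.0356, and P(|difference| > 0.05) = 2(1 − Φ(0.05/0.0356)) = 16%.
- SD of change 0.10: the cross-sectional SD is 0.10/√(2(1 − r)) = 0.129, 0.158, 0.224 at r = 0.7, 0.8, 0.9. The probability is 28%, 37%, 53%.

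**7. Adjusting for T2 sedentary level.** Assume that the arm shifts it by d = 0.25–0.5 SD and that its within-arm correlation with gait speed is c = 0.2–0.4. The estimate moves by d × c × 0.10: from 0.25 × 0.2 × 0.10 = 0.005 to 0.5 × 0.4 × 0.10 = 0.020 m/s, or 5–20% of the MCID.

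**The case against.** **The power gain may be small.** The Sample Size wording favours change. On that reading T1 adjustment lifts power only from 35% to 37–40%; the larger figures need the less natural T2-only reading. This stands. A reader might infer that the plan has been shown to lose substantial power, or that T1 adjustment restores the planned 80%. Neither follows: having only four homes is a separate limit, which adjustment does not cure.

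**The plan may intend pre-treatment covariates.** The term confounder usually means a variable fixed before treatment, and the open list could include T1 gait speed. This stands in part. A reader might infer that the trial will adjust for T2 sedentary level or will leave T1 gait speed out. The documents say neither; they leave both open. The shift in step 7 rests wholly on assumed inputs and is smaller than the standard error of 0.0356.

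**The imbalance figures are model-based.** They are probabilities over hypothetical homes and residents, not shares of the few possible allocations of these four homes. There are two homes per city, three are sister homes, and the block size is 2. If blocks were cities, which the documents do not say, both the imbalance and the degrees of freedom would change. This stands as a qualification.

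**Selection after allocation is unproven.** The same recruitment process is described for every home, so the documents do not support a claim that the arms were selected differently. Nor would ANCOVA guarantee an unbiased result if they were: ANCOVA and change rest on different untestable assumptions in that case. Blinding of T1 assessors does not settle the question.

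**Conclusion.** The concern holds as a gap in pre-specification with a cheap, better method available. No section names the analysed gait-speed variable, commits to T1 gait speed or fixes the covariates' visit.

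Its main weight is the freedom to choose between estimates that may well differ by more than half the MCID, at the probabilities in step 6. That case for fixing one model does not depend on any gain in power. The gain itself is likely but not guaranteed: the step 4 figures assume the same r within and between homes, with ICC 0.075 and 2 degrees of freedom. The T2-covariate risk is an ambiguity to close, not an error shown to be planned. The plan should be amended, but the documents do not show that its result would be biased.

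**What to change.** - State the primary analysis as ANCOVA of T2 gait speed on arm plus each resident's own T1 gait speed, in a model that accounts for home. A home-mean T1 covariate would instead use one of the two home-level degrees of freedom.
- Close the covariate list, and take age, sedentary level and any other covariate at T1 only.
- Do the same for continuous secondary outcomes that have a T1 value.
- Say how the statement that models will estimate missing values applies to a missing T1 covariate. Gaps are foreseeable: "ActivPAL data will be considered valid if the participant wears the device over at least four consecutive days", and "Participants who score 18 or above will be asked to complete subsequent questionnaires pertaining to their psychosocial health". In the second case the scale is not asked by design.
- State whether recruitment and T1 testing precede allocation of homes. If they do not, report as a limitation that neither ANCOVA nor change is guaranteed unbiased.

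Cost: no new data, one resident-level degree of freedom and a written rule for missing T1 values. There is also a possible variance rise of 2–15% against T2-only if home means do not correlate at all between visits (within-home r 0.3–0.9).
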